Vital signs	
Vital signs (blood pressure, body pulse) will be monitored as part of the physical exam as indicated in the study assessment schedule table and recorded on the clinical database.
 
After the patient has been in supine position for five minutes, systolic and diastolic blood pressure will be measured three times using an automated validated device, e.g. OMRON, with an appropriately sized cuff. The repeat measurements will be made at 1 - 2 minute intervals and the mean of the three measurements will be used. The same arm must be used throughout the study. A sphygmomanometer with an appropriately sized cuff should be used.

Body temperature	
Body temperature will be monitored as indicated in the study assessment schedule table and recorded on the clinical data base. Fever monitoring will be done every 6 hours until resolution of fever, defined as being afebrile for 24 hours.
 
Fever clearance is defined (in patients with an increased temperature at baseline) as the time of the first measurement of axillary temperature of < 37.5°C (or < 38.0°C for alternative routes). Fever clearance will be concluded following confirmation of temperature < 37.5°C (or < 38.0°C for alternative routes) on the subsequent measurement for at least 24 hours.
 
Patients who entered in the study on the basis of history of fever and did not subsequently have an increased body temperature measurement indicating presence of fever pre-dose will not be included in the analysis of FCT.

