## 12.5 Analysis of secondary endpoints

### 12.5.1 Efficacy and/or Pharmacodynamic endpoint(s)

**Secondary efficacy variables include:**

- PCR-corrected ACPR at Days 15 and 43;
- PCR-corrected ACPR at Day 29 for the Run-in Cohort, Cohort 1, and Cohort 2 separately;
- Uncorrected ACPR at Days 15, 29, and 43;
- Time to parasite clearance (PCT), defined as time from the first dose until the first total and continued disappearance of asexual parasite forms which remained at least a further 48 hours;
- Time to fever clearance (FCT), defined as time from the first dose until the first time the body temperature decreased below and remained below 37.5°C axillary or 38.0°C oral/tympanic/rectal for at least a further 24 hours;
- Proportion of patients with ETF:

- Proportion of patients with LCF;
- Proportion of patients with LPF;
- Incidence rate of recrudescence and reinfection at Days 15, 29 and 43.

Analyses of ACPRs (PCR corrected or uncorrected) will be based on the FAS and PPS. Analyses of other secondary efficacy variables will be based on the FAS. Analyses will be performed by cohort and for Cohorts 1 and 2 pooled. Note: difference between KAF156 and LUM-SDF combo and Coartem® in PCR-corrected ACPR at Day 29 is the primary efficacy endpoint (see [Section 12.4](#)).

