Fever Clearance is defined (in patients with temperature of $\geq 37.5^{\circ}\text{C}$ -axillary equivalent at baseline) as the time of the first measurement of at least 2 consecutive temperatures of $< 37.5^{\circ}\text{C}$ measured at least 24 hours apart.

Time to parasite clearance (PCT) is defined as time from the first dose until the first total and continued disappearance of asexual parasite forms which remained at least a further 48 hours

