2.7 Analysis of secondary efficacy objective(s)

2.7.1 Secondary efficacy endpoints

Secondary efficacy variables include:

1. PCR-corrected ACPR at Days 15, Day 29 (Run-in Cohort) and 43;
2. Uncorrected ACPR at Days 15, 29, and 43;
3. Proportion of patients with parasitaemia at 12, 24, and 48 hours after treatment;
4. Time to parasite clearance (PCT), defined as time from the first dose until the first total and continued disappearance of (*P. Falciparum*) asexual parasite forms which remained at least a further 48 hours;
5. Time to fever clearance (FCT), defined as time from the first dose until the first time the body temperature decreased below and remained below 37.5°C (axillary equivalent) for at least a further 24 hours;
6. Proportion of patients with early treatment failure (ETF);
7. Proportion of patients with late clinical failure (LCF);
8. Proportion of patients with late parasitological failure (LPF);
9. Incidence rate of recrudescence and new infection at Days 15, 29 and 43.

Analyses of ACPRs (PCR corrected or uncorrected) will be based on the FAS and PPS. Analyses of other secondary efficacy variables will be based on the FAS.

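### The SAP gives two conflicting event rules for fever clearance time; one of them, applied literally to 6-hourly readings, dates clearance 24 to 42 h late

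*SAP*

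**What the plan says.** Four places in the two documents define the event.

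- SAP section 2.1.1.2, the last part of the general definitions, applies to patients febrile at baseline. It dates clearance "as the time of the first measurement of at least 2 consecutive temperatures of" less than 37.5 °C, "measured at least 24 hours apart".
- SAP section 2.7.1, item 5, defines the endpoint as time from first dose "until the first time the body temperature decreased below and remained below 37.5°C (axillary equivalent) for at least a further 24 hours".
- Protocol section 12.5.1 has the same rule with route-specific thresholds: "until the first time the body temperature decreased below and remained below 37.5°C axillary or 38.0°C oral/tympanic/rectal for at least a further 24 hours".
- Protocol Table 8-4 dates clearance at the first reading below the threshold and requires confirmation "on the subsequent measurement for at least 24 hours".

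The measurement schedule is in protocol Table 8-4: "Fever monitoring will be done every 6 hours until resolution of fever, defined as being afebrile for 24 hours". The footnotes to protocol Tables 8-1 to 8-3 repeat it, and the note under SAP Table 5-6 acknowledges the 6-hourly checks. The temperature rows of Tables 8-1 to 8-3 add fixed readings at 0, 24, 30, 36, 48 and 72 h, then at 96 h, 168 h and later visits.

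SAP section 2.7.2.4 describes the analysis: Kaplan-Meier summaries, an exploratory log-rank test and censoring rules. It does not restate the event or say which definition governs. SAP section 4 declares no change from the protocol's analyses.

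**The concern.** The two SAP rules ask for different things. Section 2.7.1 asks that the temperature stay down for 24 h and puts no condition on the gap between neighbouring readings. Section 2.1.1.2, taken at its word, asks for consecutive readings that are themselves 24 h apart. While fever is being monitored, consecutive readings are 6 h apart, so that condition can be met only after monitoring has stopped and the visits have spread out.

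A programmer could reasonably work from either place. Section 2.1.1.2 sits under the general definitions, where derivation rules are expected. The SAP words parasite clearance time in nearly the same way in both sections, but words fever clearance differently.

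Under the literal rule, fever clearance time would largely record when visit spacing widened, not when fever ended. Early clearances would be tied, and the Kaplan-Meier summaries and the log-rank comparison would lose most of the information in the 6-hourly readings.

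**Working it through.** The plan gives no power, effect size or event count for fever clearance time, so there is no stated figure to reproduce. The check is to date clearance under each rule for a known end of fever.

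**Inputs.** Let T be the first afebrile reading, on the 6-hourly grid. Readings are every 6 h up to T + 24 h (protocol Table 8-4), plus the fixed readings at 24, 30, 36, 48, 72, 96 and 168 h (protocol Tables 8-1 to 8-3). Clearance is assumed to be sustained, and clock times exact.

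**Rule A (SAP 2.7.1, protocol 12.5.1).** The first afebrile reading after which all readings over at least the next 24 h are afebrile. This gives T itself for every T.

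**Rule B (SAP 2.1.1.2, adjacent-pair reading).** The first afebrile reading t(i) for which t(i+1) − t(i) ≥ 24 h.

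- T = 6 h: readings are 6, 12, 18, 24, 30, 36, 48, 72 h. The gaps are 6, 6, 6, 6, 6, 12 and 24 h. The first gap of 24 h starts at 48 h.
- T = 30 h: 6-hourly readings run to 54 h, so 54 h falls between 48 and 72 h and splits that interval into 6 h and 18 h. The first qualifying gap is 72 to 96 h, so the result is 72 h.
- T = 54 h: 6-hourly readings run to 78 h and split 72 to 96 h into 6 h and 18 h. The first qualifying gap is 96 to 168 h, so the result is 96 h.

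| Fever ends (T) | Rule A | Rule B | Rule B minus T |
|---|---|---|---|
| 6, 12, 18, 24 h | T | 48 h | 42, 36, 30, 24 h |
| 30, 36, 42, 48 h | T | 72 h | 42, 36, 30, 24 h |
| 54, 60, 66, 72 h | T | 96 h | 42, 36, 30, 24 h |
| 78, 84, 90, 96 h | T | 102, 108, 114, 120 h | 24 h each |

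**Effect on a comparison.** Children clearing at 6 h and at 24 h differ by 18 h but are tied at 48 h. Children clearing at 24 h and at 30 h differ by 6 h but are dated 48 h and 72 h, which is 24 h apart.

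**Sensitivity to clock time.** If the second-day and third-day readings fall at 48.2 h and 72.0 h, the gap is 72.0 − 48.2 = 23.8 h and no longer qualifies. The tested cases T = 6, 18 and 36 h are then all dated 72 h.

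**Windowed values.** On the SAP Table 5-6 timepoints (6, 12, 24, 36, 48, 72 h, plus 96 and 168 h), Rule B dates every T up to 48 h at 48 h. Rule A also becomes coarser: T = 18 h is dated 24 h, T = 30 h is dated 36 h, and T = 54 h is dated 72 h. The choice of readings therefore matters under either rule.

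**The case against.** The strongest reply is that the endpoint itself is already defined correctly. SAP 2.7.1 is where the secondary endpoints are set out, it agrees with protocol 12.5.1, and under it clearance is dated at the first afebrile reading. The 2.1.1.2 sentence can also be read in agreement: a run of at least two consecutive afebrile readings spanning 24 h, dated at its first reading. That is the structure of protocol Table 8-4, of which the sentence may be a condensed version.

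This stands as far as it goes. A reader might infer that every child's fever clearance time will be pushed to 48 h or 72 h. The documents do not support that, for four reasons: 2.7.1 gives a rule with no shift; the sentence has a second possible reading; even under the adjacent-pair reading, fever ending after 48 h is dated 96 h or later; and children without fever before dosing are not in this analysis, while others may be censored.

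The stakes are also limited. SAP 2.7.2 calls the secondary endpoints supportive, without pre-specified hypotheses, and 2.7.2.4 calls the log-rank comparison exploratory, although protocol 12.5.1 sets a two-sided 5% level for it.

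On the windows, SAP 5.1.4 uses mapped visits for by-visit analyses, and nothing says fever clearance time is built from them. Naming the readings is therefore a clarification, not a correction.

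The reply does not remove the conflict. Two differently worded rules stand in one SAP, nothing ranks them, and the adjacent-pair reading is the more literal one for 2.1.1.2.

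**Conclusion.** The concern holds as an internal conflict in the SAP that could be programmed wrongly. It does not show that the plan as a whole misdates fever clearance.

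If 2.1.1.2 is applied to adjacent readings, an individual time is dated 24 to 42 h late for fever ending between 6 and 96 h, with ties at 48, 72 and 96 h. If 2.7.1 is applied to all readings, the shift is zero. These figures assume 6-hourly readings until the child has been afebrile for 24 h, exact clock times and sustained clearance. I put no figure on the medians or on lost power, because the documents give no distribution of clearance times.

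The point is worth correcting because a stated derivation rule for a named secondary endpoint gives wrong times if followed literally, and the SAP declares no departure from the protocol. The primary endpoint and the sample size do not use fever clearance time.

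**What to change.** Replace the fever clearance sentence in SAP 2.1.1.2 with the rule in SAP 2.7.1 and protocol 12.5.1: the time of the first reading below 37.5 °C (axillary equivalent) after which all readings over at least the next 24 h are also below 37.5 °C. Refer to that single definition from 2.7.2.4.

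Add that fever clearance time uses all temperature readings, not the windowed values of SAP Table 5-6, with actual times where captured and planned times where the actual time is missing. The second part is needed because SAP 2.1.1 says the database did not capture clock times for temperature in the Run-in Cohort and its repeats.

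The cost is one replaced sentence and one added sentence in the SAP, plus a check that the derivation program follows them. No new data are needed, and the protocol does not change.

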2.2 Analysis sets

Randomized set

All patients who are randomized into the study.

Full analysis set (FAS)

FAS will be comprised of all patients from Randomized set who take at least one dose of study treatment during the treatment period and whose baseline *P. Falciparum* asexual parasitaemia count is greater than 0. Following the intent-to-treat principle, patients will be analyzed according to the treatment group assigned to at randomization.

Unless otherwise specified, misrandomized patients will be excluded from the FAS.

Misrandomized patients, if identified from IRT, include patients who are screen-failures, but have been randomized by the investigator before eligibility was finally assessed or mistakenly, and have not been treated. If patients were re-screened and successfully randomized, they will be included in the randomized set according to the treatment assigned in the last randomization.

Safety set (SAF)

Safety set includes all patients who take at least one dose of study drug during the treatment period. Patients will be analyzed according to treatment received. In particular, patient will be analyzed in the same treatment group as randomized if s/he receives at least one dose of the study medication of that group. For the PK run-in cohort, all patients to receive the same dose in either fasted or fed condition.

Per-protocol set (PPS)

Per-protocol set will be comprised of patients in FAS who

- did not have any important protocol deviations affecting efficacy
- took at least 80% dosages of randomized study medication(s). If a patient vomited the original dose but did not vomit the replacement dose, the patient is considered as taking the dose of study medication. Since a partial compliance, such as 83%, etc., can be calculated based on the actual dosage taken (see [Section 2.4.1](#)), this allows patients to take partial dosages.
- did not take non-study medications with anti-malaria activity prior to Day 29 visit unless experiencing any treatment failure (ETF, LCF, LPF) (e.g new infections between Day 8 and Day 29), and PCR corrected ACPR status at Day 29 is defined, ie, at least one of the following criteria is met:
 - a. classified as treatment failure before Day 8 (see [Section 2.1.1](#))
 - b. had parasitaemia present on Day 8 or later without parasite clearance before (eg., parasite present Day 15 and parasite was not cleared before Day 15).
 - c. absent from parasitaemia at Day 29 or later,
 - d. had a recrudescence if parasitaemia is present from Day 8 to Day 29, or
 - e. had a new infection at Day 29 visit or later

Food noncompliance in the Run-in cohort is considered as important PD. Important protocol deviations for exclusion from PPS are specified in [Table 5-14](#) and will be identified by the clinical team before the database lock.

PK analysis set

Run-in Cohort

PK Analysis set: All the subjects in the safety analysis set who have at least one evaluable PK concentration. A profile is considered evaluable for that period if following conditions are satisfied:

- Participants took at least 80% dosages of randomized study medication
- If a patient vomited the original dose but did not vomit the replacement dose
- Participants with no protocol deviations (PD) that may have an impact on the PK data

PK analysis set-partial food compliance: all subjects in the PK analysis set who are compliant to meal criteria (within 30 minutes of drug administration and took at least 70% of the standard meal) on any of the two dosing days.

PK analysis set-Full food compliance: all subjects in the PK analysis set who are compliant to meal criteria (within 30 minutes of drug administration and took at least 70% of the standard meal) on both dosing days.

Note that meal non-compliance for the run-in cohorts is identified using the PD (protocol deviation) code OTH04.

Cohort 1 and Cohort 2

PK Analysis set: All the subjects in the safety analysis set who have at least one evaluable PK concentration. A profile is considered evaluable for that period if following conditions are satisfied:

- Participants took at least 80% dosages of randomized study medication
- If a patient vomited the original dose but did not vomit the replacement dose
- Participants with no protocol deviations (PD) that may have an impact on the PK data

PK analysis set-partial food compliance*: all subjects in the PK analysis set who are compliant to meal criteria (within 1 hour (± 5 min) of drug administration and took at least 70% of light meal) on both Days 2 and 3.

PK analysis set-Full food compliance*: All subjects in the PK analysis set who are compliant to meal criteria (within 1 hour (± 5 min) of drug administration and took at least 70% of light meal) on all three dosing days.

*: In breastfed subjects, the % is not considered (as it cannot be assessed) and breastfeeding within the ± 1 hr (± 5 min) of dosing is considered as meeting the criteria for both standard and light meal.

Note that meal non-compliance for Cohort 1 and Cohort 2 is identified using PD code OTH04A.

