#### **6.7.2 Instruction for prescribing and taking study treatment**

##### **KAF156 and LUM-SDF**

Patients will take the KAF156 and LUM-SDF according to the assigned dose level and dosing regimen of the KAF156 and LUM-SDF combination.

LUM-SDF will be given as a dispersible powder directly in the mouth and then patients should drink some water. Subsequently (preferably in 2 min, but in any case < 15 min), KAF156 will be given as film-coated tablets that could be dissolved in some water. Administration of LUM-SDF and KAF156 must be done under study staff supervision.

Each patient's mouth must be examined to verify that the medications were swallowed. In the case that the patient vomits within 1 hour of intake, a replacement dose will be given to the patient and the investigator or designee will notify IRT. If the second dose is vomited the patient has to be given alternative treatment preferably not containing lumefantrine.

Patients who will be administered treatment under fasting condition should be fasted at least 4 hours before and 4 hours after KAF156/LUM-SDF administration. However, these patients can receive non-fatty liquids such as orange juice prior to 1 hour of dosing and 1 hour after dosing. All food intake has to be recorded appropriately. Water can be provided ad-libitum.

Patients who will be administered treatment with food should have food within 30 min (preferably prior to dose) of dose administration.

Patients in the Run-in Cohort who have been randomized to the Fed group should consume food containing 400-500 calories and 20-30 g of fat (standard meal).

This recommendation for food may be adapted based on the evaluation of the food effect in the Run-in Cohort. Such change will be based on the observed Cmax of lumefantrine. All investigators will be informed in case of an adaptation in food recommendation.

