## Coartem®

With respect to Coartem®, patients will be dosed BID for 3 days (at the following time points: 0, 8, 24, 36, 48, and 60 hours) and must receive a standard meal less than 30 min prior to dosing, as per label. Dosages will be administered according to weight group as described in [Table 6-4](#).

The dispersible tablet is to be dissolved in 10 mL of water in a small cup, and subsequently administered orally under hospital supervision; thereafter the cup will be rinsed with an additional 10 mL of water and the content is to be swallowed again. This procedure will be repeated as necessary in order to administer the amount of doses indicated.

Coartem® medication should be followed whenever possible by food/drink (mother's milk, broth, sweetened condensed milk, etc.) as appropriate.

For all treatment groups, food intake information will be collected only on each dosing day, i.e., time of last food intake before dosing, time of the first food intake after dosing, amount of meal consumed (%) and type of food based on the following 6 categories:

1. None (=no meal)
2. Liquid only (zero fat)
3. Minimal meal (estimate of < 100 calories, ~ 1 g of fat)
4. Light meal (estimate of 100-300 calories, 5-10 g of fat)
  - 4a. ~250 mL of whole milk
  - 4b. Breastfed/formula milk
  - 4c. Porridge
  - 4d. Pancake
  - 4e. Other
5. Standard meal (estimate of 400-500 calories, 20-30 g of fat)
6. High fat meal (estimate of 800-1000 calories, > 50 g of fat)

[figure not shown]
A low fat vehicle such as orange juice may be used for drug administration in children who are unable to take the medication normally with water.

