Analyses will be performed using the PK analysis set, PK analysis set-partial food compliance, and PK analysis set-full food compliance (see Section 2.2 for the definition).

Note that in the PK analysis set-partial food compliance for the run-in cohorts, only the PK concentrations from the dosing day, where subjects are compliant to the meal criteria, will be included in the analysis.

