5.8 Rule of exclusion criteria of analysis sets

Table 5-14 Protocol deviations and non-PD criteria leading to exclusion from analysis sets

Analysis Set	PD (Description and ID) that causes Patients to be excluded	Non-PD criteria that cause Patients to be excluded
Randomized	
 Informed Consent for study participation or parental consent not obtained and patient entered trial (INCL05) 	
 Not randomized Misrandomized if identified from IRT
FAS	NA	
 Not in Randomized set Baseline parasitaemia count is 0 or missing No study drug taken
PPS	
 Parasite specie is other than Plasmodium falciparum OR mixed infection (INCL03) Baseline plasmodium falciparum parasite count <1000/uL or ≥150000/uL (INCL04) at the time of prescreening for the Run-in; plasmodium falciparum parasite count < 1,500 or ≥ 150,000 /uL parasites/μL at the time of pre-screening for Cohorts 1 and 2 No fever within the past 24 hours at baseline (INCL06) Prohibited non-antimalarial medications that may have effect on efficacy if received before the Day 29 visit without being falciparum treatment failures (COMD001A) Only for Run-in Cohort, do not fully comply with the food guidelines according to randomization (with OTH04 either day) 	
 Not in FAS; <80% of randomized study medication taken Received non-study concomitant antimalarial drugs during the treatment period Received non-study concomitant antimalarial drugs after the treatment period between Day 4 and Day 29 without experiencing treatment failure Not classified as non-responder before Day 8, no positive blood smear parasite on Day 8 onwards, and blood smear parasite result is missing at Day 29 and later (early discontinued) Not classified as non-responder before Day 8, have at least one positive blood smear parasite result between Day 8 and Day 29 which cannot be determined as recrudescent or new infection based on PCR genotyping and have parasites cleared prior to the positive blood smear parasite; Not classified as non-responder before Day 8, have a new infection prior to study Day 27 and have

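### The food-compliance PK sets in SAP 2.2 use meal criteria that do not match the assigned food condition, for the fasted Run-in arm and for the Coartem arm

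*SAP*

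**What the plan says.** **Run-in Cohort.** SAP 2.2 defines the stricter set as "PK analysis set-Full food compliance: all subjects in the PK analysis set who are compliant to meal criteria", and the criterion reads in full: "compliant to meal criteria (within 30 minutes of drug administration and took at least 70% of the standard meal) on both dosing days". The partial-compliance set needs the same on either day. Neither definition is limited to the fed arm. SAP 2.2 then says that Run-in meal non-compliance is picked up by deviation code OTH04. Table 5-14 (SAP 5.8) describes that code, as a reason for exclusion from the PPS, in these words: "Only for Run-in Cohort, do not fully comply with the food guidelines according to randomization (with OTH04 either day". Protocol 6.7.2 says that patients in the fasted arm "should be fasted at least 4 hours before and 4 hours after KAF156/LUM-SDF administration".

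**Cohorts 1 and 2.** The full-compliance set takes all subjects who ate within 1 hour (±5 min) of dosing and "took at least 70% of light meal) on all three dosing days". The partial set asks for this on Days 2 and 3. There is no split by arm. Non-compliance is picked up by code OTH04A, which neither document defines. For Coartem, protocol 6.7.2 says that patients "must receive a standard meal less than 30 min prior to dosing, as per label".

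**Use.** SAP 2.9 states: "Analyses will be performed using the PK analysis set, PK analysis set-partial food compliance, and PK analysis set-full food compliance". It plans the Run-in fed/fasted geometric mean ratio with a 90% CI. Protocol 12.5.3 plans the between-arm lumefantrine ratio in Cohorts 1 and 2.

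**The concern.** A food-compliance set should keep patients who followed the food condition assigned to them. These sets instead ask whether the patient ate a particular meal. That is the right question for the Run-in fed arm, the opposite of the right question for the fasted arm, and a different question from the protocol's for Coartem.

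The food effect on lumefantrine is the main objective of the Run-in Cohort (SAP 3.1.2), and these sets are meant to show it in patients who complied. In Cohorts 1 and 2 a reader would take the label of full food compliance to mean that the Coartem patients were fed as the protocol requires. The written criterion does not establish that.

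**Working it through.** **1. The plan's own precision for the fed/fasted ratio.** Inputs from SAP 3.1.2: SD 0.69 for log Cmax, SD 0.77 for log AUC0-24h, target 90% CI half-width w = 0.693 (ln 2), 24 randomised, 20% not evaluable. The probability that the half-width is at most w, with n per arm, is P(χ² with 2n−2 df ≤ (2n−2)·n·w² / (2·t²·SD²)).

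- Cmax, n = 8: 14 × 8 × 0.4805 / (2 × 1.761² × 0.4761) ≈ 18.2 on 14 df, giving 80.3% (plan: 80%). For n = 9 the result is 90.7% (plan: 90%).
- AUC, n = 10: 18 × 10 × 0.4805 / (2 × 1.734² × 0.5929) ≈ 24.3 on 18 df, giving 85.3%. For n = 9 it is 73.9%, so 10 is the smallest n that reaches the plan's 80%.
- Evaluable per arm: 24 × 0.8 / 2 = 9.6 (plan: 9 to 10).

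The plan's sample sizes reproduce. They need about 9 to 10 patients in each arm, including the fasted arm.

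**2. Run-in membership under the two rules in the SAP.** Eating most of a standard meal within 30 minutes of dosing cannot be combined with 4 hours without food on either side, so the outcomes are fixed:

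| Patient | Written meal criterion | OTH04, by randomised condition |
|---|---|---|
| Fed arm, ate the meal | in | in |
| Fed arm, did not eat it | out | out |
| Fasted arm, kept the fast | out | in |
| Fasted arm, wrongly ate the meal | in | out |

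The rules agree for the fed arm and give opposite answers for both kinds of fasted patient. Under the written criterion the sets hold 0 adherent fasted patients, against up to about 9.6 fed patients. Any fasted-arm data left would come from patients who ate. SAP 2.9 sharpens this for the Run-in partial set, because only concentrations from days that meet the meal criterion are used. A fasted patient who ate on one day would contribute that day alone. Under OTH04 about 9.6 per arm remain before food exclusions, which matches step 1.

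**3. Coartem criterion against the protocol.** Meal categories from protocol 6.7.2: light meal 100-300 calories and 5-10 g fat; standard meal 400-500 calories and 20-30 g fat.

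| | SAP threshold: 70% of a light meal | 70% of a standard meal |
|---|---|---|
| Calories | 0.70 × 100-300 = 70-210 | 0.70 × 400-500 = 280-350 |
| Fat | 0.70 × 5-10 = 3.5-7 g | 0.70 × 20-30 = 14-21 g |
| Timing | within 1 h (±5 min), so up to 65 min | protocol: less than 30 min before the dose |

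The fat ratio runs from 14/7 = 2 to 21/3.5 = 6. The 70% applied to the standard meal is borrowed from the SAP's Run-in criterion, since the protocol states no percentage for Coartem. The SAP set therefore holds Coartem patients who met the protocol meal rule together with patients who missed its meal type, its timing or both.

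**The case against.** **OTH04 may be the operative rule.** SAP 2.2 says that non-compliance is identified by that code, and under it an adherent fasted patient stays in. This stands. A reader might infer that fasted patients can never enter these sets. The documents do not support that, because one of the two rules admits them. What remains is that the set definitions state only an eating criterion, so two programmers could build opposite fasted arms from the same SAP.

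**OTH04A may be specific to each arm.** This cannot be excluded. A reader might take the code as support for the light-meal definition, but it is undefined and supports neither reading. The footnote on breastfed children, attached to the Cohort 1 and 2 sets, says that breastfeeding satisfies both the standard-meal and the light-meal criterion. Those definitions contain no standard-meal criterion. Either one was left out or one operates out of sight. The food advice issued after the Run-in Cohort is not in the documents either. The clause allowing such adaptation stands under the KAF156/LUM-SDF heading of protocol 6.7.2, while Coartem stays as labelled.

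**The consequences are limited.** This also stands. The main PK set in SAP 2.2 has no stated meal criterion, so the fed/fasted ratio can be estimated there. The food-compliance sets came in with the June 2024 SAP update, after the dry run, so they could not have driven the dose and food decision taken before Cohort 1. Protocol 12.3 already plans a summary of meal intake and type by day, which would show how Coartem patients were fed.

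**Non-inferiority.** A reader might infer that the loose Coartem criterion biases the primary comparison. It does not. The test uses the PPS, whose food exclusion applies to the Run-in Cohort only, and a set label does not change what a child ate or absorbed.

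**Conclusion.** The point holds as a defect in the written set definitions. In the Run-in Cohort the stated meal criterion contradicts the fasting rule in protocol 6.7.2 and the use of OTH04 in Table 5-14. Read literally, it leaves no adherent fasted patient in either food-compliance set and so no valid fed/fasted ratio there. In Cohorts 1 and 2 the stated criterion labels Coartem patients as fully compliant on a meal with 2 to 6 times less fat than the same share of a standard meal, and at up to 65 minutes from dosing.

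The effect is confined to the supplementary food-compliance PK analyses: the Run-in fed/fasted ratio, and lumefantrine exposure by arm in Cohorts 1 and 2. The main PK set, the PPS and the primary test are untouched.

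The conclusion assumes that the SAP text, and not an unseen deviation specification, governs membership. I do not convert the fat difference into an exposure difference. The protocol's fold increases with food (section 4.2) are preliminary healthy-volunteer data from the LUM-SDF programme, the protocol expects a smaller effect in patients, and carrying them over to Coartem would be an assumption. Nothing here says which meal rule is clinically right.

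**What to change.** In SAP 2.2, define food compliance against the assigned condition:

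- Run-in fed arm: keep the current text.
- Run-in fasted arm: use the fasting rule of protocol 6.7.2, including the liquids it allows.
- Cohorts 1 and 2: state a criterion for each treatment arm. For KAF156/LUM-SDF, cite the recommendation issued after the Run-in Cohort. For Coartem, reconcile SAP 2.2 with protocol 6.7.2 so that both give the same meal type and timing.
- Define OTH04 and OTH04A in Table 5-14 to match, and align the breastfeeding footnote.

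Then repeat the planned PK summaries in the corrected sets. Two extensions are not proposed. A check at each of the six Coartem doses is not shown to be feasible, since the assessment schedules list the meal record once per dosing day. A comparison of ACPR in food-compliant patients would select on behaviour after randomisation, by a different rule in each arm.

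The cost is SAP wording and reprogramming of the food-compliance flags. Meal type, percentage eaten and times are already collected on each dosing day (protocol 6.7.2). The downside is that the Coartem food-compliant subset may be smaller.
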